8.3.4 Clinical Safety Laboratory Assessments

Refer to Appendix 2 for the list of clinical laboratory tests to be performed and to the SoA for the timing and frequency.

- The investigator or medically qualified designee (consistent with local requirements) must review the laboratory report, document this review, and record any clinically relevant changes occurring during the study in the AE section of the case report form (CRF). The laboratory reports must be filed with the source documents. Clinically significant abnormal laboratory findings are those which are not associated with the underlying disease, unless judged by the investigator to be more severe than expected for the participant's condition.
- All protocol-required laboratory assessments, as defined in Appendix 2, must be conducted in accordance with the SoA.
- If laboratory values from nonprotocol specified laboratory assessments performed at the institution's local laboratory require a change in study participant management or are considered clinically significant by the investigator (eg, SAE or AE or dose modification), then the results must be recorded in the appropriate CRF (eg, SLAB).
- For any laboratory tests with values considered clinically significantly abnormal during participation in the study or within 14 days after the last dose of study intervention, every attempt should be made to perform repeat assessments until the values return to normal or baseline or if a new baseline is established as determined by the investigator.

8.3.5 Pulmonary Function Tests (PFTs (Spirometry))

At all visits (except Part 2, Periods 2 and 3), PFTs should be performed as per the SoA.

Spirometry should be performed in accordance with guidelines established by the American Thoracic Society/European Respiratory Society (ATS/ERS) Standardization of Lung Function Testing: Standardization of Spirometry; 2005 [American Thoracic Society 2005].

Additional details regarding spirometry procedures will follow manufacturer's instructions and site SOPs. Every attempt must be made to use one spirometer consistently on each participant. The spirometry should be performed with the participant sitting in a chair with arms and no wheels; however, if it is necessary to test the participant standing or in another position, this should be noted on the spirometry report. The participant position should be consistent throughout the study.

At least three measurements (to obtain 2 reproducible) for FEV₁ and FVC will be performed at each scheduled time point. The largest FEV₁ and the largest FVC should be recorded after the data are examined from all of the acceptable measurements, even if they do not come from the same measurement.

The site normal ranges are to be used to determine percent predicted.

The spirometer is to be calibrated following the principles of the ATS/ERS Guidelines and the device manual on the days when spirometry is performed. The calibration records should be kept in a reviewable log.

It is preferred that the calibration equipment that is used to calibrate the spirometer be subjected to a validated calibration according to the manufacturer's specifications.

The following pulmonary function tests: (FEV₁, FVC and FEV₁/FVC ratio, PEF), DLCO (DLCO, DLCO adjusted for Hb and DLCO/VA) and lung volume (TLC, VC, IC, FRC and RV) will be captured by the pulmonary function lab as per their standard procedures at the screening visit.

Spirometry (FEV₁, FVC and FEV₁/FVC ratio, PEF) will be done at all other timepoints noted in the SoA and will be done at the site using calibrated spirometers.

8.3.6 Inhalation Airflow Meter Assessment

At least 3 measurements (at least 3-5 minutes apart) for inspiratory flow rate will be performed at timepoints as per the study flowchart.

The meter is to be reset following each measurement as per the instructions in the device manual. All measurements obtained will be recorded.

8.4 Adverse Events (AEs), Serious Adverse Events (SAEs), and Other Reportable Safety Events

The definitions of an AE or SAE, as well as the method of recording, evaluating, and assessing causality of AE and SAE and the procedures for completing and transmitting AE, SAE, and other reportable safety event reports can be found in Appendix 3.

Adverse events, SAEs, and other reportable safety events will be reported by the participant (or, when appropriate, by a caregiver, surrogate, or the participant's legally authorized representative).

The investigator and any designees are responsible for detecting, documenting, and reporting events that meet the definition of an AE or SAE as well as other reportable safety events. Investigators remain responsible for following up AEs, SAEs, and other reportable safety events for outcome according to Section 8.4.3.

The investigator, who is a qualified physician, will assess events that meet the definition of an AE or SAE as well as other reportable safety events with respect to seriousness, intensity/toxicity and causality.

8.4.1 Time Period and Frequency for Collecting AE, SAE, and Other Reportable Safety Event Information

AEs, SAEs, and other reportable safety events that occur after the consent form is signed but before intervention allocation/randomization, must be reported by the investigator for randomized participants only if the event is the result of a protocol-specified intervention, including but not limited to washout or discontinuation of usual therapy, diet, placebo treatment, or a procedure.

From the time of intervention allocation/randomization through 14 days following cessation of intervention, all AEs, SAEs and other reportable safety events must be reported by the investigator.

Additionally, any SAE brought to the attention of an investigator any time outside of the time period specified in the previous paragraph also must be reported immediately to the Sponsor if the event is considered drug-related.

Investigators are not obligated to actively seek AEs or SAEs or other reportable safety events in former study participants. However, if the investigator learns of any SAE, including a death, at any time after a participant has been discharged from the study, and he/she considers the event to be reasonably related to the study intervention or study participation, the investigator must promptly notify the Sponsor.

All initial and follow-up AEs, SAEs, and other reportable safety events will be recorded and reported to the Sponsor or designee within the time frames as indicated in [Table 4](#).

Table 4 Reporting Time Periods and Time Frames for Adverse Events and Other Reportable Safety Events

Type of Event	Reporting Time Period: Consent to Randomization/ Allocation	Reporting Time Period: Randomization/ Allocation through Protocol-specified Follow-up Period	Reporting Time Period: After the Protocol-specified Follow-up Period	Time Frame to Report Event and Follow-up Information to Sponsor:
Nonserious Adverse Event (NSAE)	Report if: - due to protocol-specified intervention - causes exclusion - participant is receiving placebo run-in or other run-in treatment	Report all	Not required	Per data entry guidelines
Serious Adverse Event (SAE)	Report if: - due to protocol-specified intervention - causes exclusion - participant is receiving placebo run-in or other run-in treatment	Report all	Report if: - drug/vaccine related. (Follow ongoing to outcome)	Within 24 hours of learning of event
Pregnancy/ Lactation Exposure	Report if: - due to intervention - causes exclusion	Report all	Previously reported – Follow to completion/termination; report outcome	Within 24 hours of learning of event
Event of Clinical Interest (require regulatory reporting)	Report if: - due to intervention - causes exclusion	Report - potential drug-induced liver injury (DILI) - require regulatory reporting	Not required	Within 24 hours of learning of event
Event of Clinical Interest (do not require regulatory reporting)	Report if: - due to intervention - causes exclusion	Report - non-DILI ECIs and those not requiring regulatory reporting	Not required	Within 5 calendar days of learning of event
Cancer	Report if: - due to intervention - causes exclusion	Report all	Note required	Within 5 calendar days of learning of event
Overdose	Report if: - receiving placebo run-in or other run-in medication	Report all	Note required	Within 24 hours of learning of event

8.4.2 Method of Detecting AEs, SAEs, and Other Reportable Safety Events

Care will be taken not to introduce bias when detecting AEs and/or SAEs and other reportable safety events. Open-ended and nonleading verbal questioning of the participant is the preferred method to inquire about AE occurrence.

8.4.3 Follow-up of AE, SAE, and Other Reportable Safety Event Information

After the initial AE/SAE report, the investigator is required to proactively follow each participant at subsequent visits/contacts. All AEs, SAEs, and other reportable safety events including pregnancy and exposure during breastfeeding, events of clinical interest (ECIs), cancer, and overdose will be followed until resolution, stabilization, until the event is otherwise explained, or the participant is lost to follow-up (as defined in Section 7.3). In addition, the investigator will make every attempt to follow all nonserious AEs that occur in randomized participants for outcome. Further information on follow-up procedures is given in Appendix 3.

8.4.4 Regulatory Reporting Requirements for SAE

Prompt notification (within 24 hours) by the investigator to the Sponsor of SAE is essential so that legal obligations and ethical responsibilities towards the safety of participants and the safety of a study intervention under clinical investigation are met.

The Sponsor has a legal responsibility to notify both the local regulatory authority and other regulatory agencies about the safety of a study intervention under clinical investigation. The Sponsor will comply with country-specific regulatory requirements and global laws and regulations relating to safety reporting to regulatory authorities, IRB/IECs, and investigators.

Investigator safety reports must be prepared for suspected unexpected serious adverse reactions (SUSARs) according to local regulatory requirements and Sponsor policy and forwarded to investigators as necessary.

An investigator who receives an investigator safety report describing an SAE or other specific safety information (eg, summary or listing of SAE) from the Sponsor will file it along with the IB and will notify the IRB/IEC, if appropriate according to local requirements.

8.4.5 Pregnancy and Exposure During Breastfeeding

Although pregnancy and infant exposure during breastfeeding are not considered AEs, any pregnancy or infant exposure during breastfeeding in a participant (spontaneously reported to the investigator or their designee) that occurs during the study are reportable to the Sponsor.

All reported pregnancies must be followed to the completion/termination of the pregnancy. Pregnancy outcomes of spontaneous abortion, missed abortion, benign hydatidiform mole, blighted ovum, fetal death, intrauterine death, miscarriage, and stillbirth must be reported as serious events (Important Medical Events). If the pregnancy continues to term, the outcome (health of infant) must also be reported.

8.4.6 Disease-related Events and/or Disease-related Outcomes Not Qualifying as AEs or SAEs

Disease related events and or disease related outcomes not qualifying as AEs or SAEs are not applicable to this study.

8.4.7 Events of Clinical Interest (ECIs)

Selected nonserious and SAEs are also known as ECIs and must be reported to the Sponsor.

Events of clinical interest for this study include:

- An overdose of Sponsor's product, as defined in Section 8.5, that is not associated with clinical symptoms or abnormal laboratory results.
- An elevated AST or ALT lab value that is greater than or equal to 3X the upper limit of normal and an elevated total bilirubin lab value that is greater than or equal to 2X the upper limit of normal and, at the same time, an alkaline phosphatase lab value that is less than 2X the upper limit of normal, as determined by way of protocol-specified laboratory testing or unscheduled laboratory testing.*

*Note: These criteria are based upon available regulatory guidance documents. The purpose of the criteria is to specify a threshold of abnormal hepatic tests that must trigger an additional evaluation for an underlying etiology. The study site guidance for assessment and follow up of these criteria can be found in the Investigator Study File Binder (or equivalent).

It may also be appropriate to conduct additional evaluation for an underlying etiology in the setting of abnormalities of liver blood tests including AST, ALT, bilirubin, and alkaline phosphatase that do not meet the criteria noted above. In these cases, the decision to proceed with additional evaluation will be made through consultation between the study investigators and the Sponsor Clinical Director. However, abnormalities of liver blood tests that do not meet the criteria noted above are not ECIs for this study.

8.5 Treatment of Overdose

The participant has taken (accidentally or intentionally) any drug administered as part of the protocol that exceeds the dose as prescribed by the protocol. It is up to the investigator or the reporting physician to decide whether a dose is to be considered an overdose, in consultation with the Sponsor.

8.6 Pharmacokinetics

The decision as to which plasma samples collected will be assayed for evaluation of PK/pharmacodynamics will be collaboratively determined by the Sponsor (eg, samples at lower doses may not be assayed if samples at higher doses reveal undetectable drug

concentrations). If indicated, these samples may also be assayed and/or pooled for assay in an exploratory manner for metabolites and/or additional pharmacodynamic markers.

8.6.1 Blood Collection for Plasma MK-5475

Sample collection, storage, and shipment instructions for plasma samples will be provided in the study operations manual.

8.7 Pharmacodynamics

Pharmacodynamic assessments that are part of the right heart catheterization (RHC) and the functional respiratory imaging (FRI) procedures will be performed according to the Study Operations and CT scan procedures manuals.

8.7.1 Right Heart Catheterization Procedures

Before beginning the RHC procedure, monitoring equipment should be calibrated and zeroed.

Pressure measurements should be taken at end-expiration and should include at least 3 complete respiratory cycles. Pressures measured at each study time point will include right atrium pressure (RAP), right ventricular systolic and end diastolic pressure (RVSP, RVEDP), pulmonary artery wedge pressure (PAWP), and pulmonary artery pressure (PAP) (systolic, diastolic or mean). Cardiac output (CO), oxygen saturation and MVO₂ will also be collected at timepoints noted in the SoA.

Investigators may use clinical judgment to determine whether the central catheter may be maneuvered during the catheterization procedure for the purpose of measuring RAP, RVSP, and RVEDP. If the investigator determines that the participant's condition prohibits the maneuvering of the catheter during the procedure, the catheter may remain in place for the measurements of PAWP, sPAP/dPAP or mPAP, and CO.

Participants will undergo monitoring of systemic hemodynamics and for adverse events throughout the RHC. The study-related portion of RHC will continue until completion of all measurements at the 4.5 hr postdose timepoint after which it may be removed unless clinically indicated it is needed to stop earlier.

Waveform analysis will be performed through the use of a blinded central reader.

Standard operating procedures for RHC will be developed with the site. All specifications and details will be provided in the Study Operational Manual.

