Urine Pregnancy Test (WOCBP only)	X										See Appendix 10.2 for details regarding laboratory tests. Pre-dose lab tests may occur w/in 24 hrs of baseline scan	
Hematology/Chemistry	X									X		
Urinalysis	X									X		
PT/aPTT	X									X		
PFTs										X		
AE/SAE review	X	X	X	X	X	X	X	X	X	X	See all sections under 8.4	
Pharmacokinetics												
Blood for Plasma MK-5475 and or Metabolites Assay	X		X-----X									Panels A, B and C: Predose, 1, 3, 8 and 24 hours postdose. Panel D: Predose, 15 min, 30 min, 1, 2, 3, 4, 8 and 24 hours postdose See operations manual for sample processing details
Pharmacodynamics												
CT Scan for Functional Respiratory Imaging (FRI)		X		X	X	X			X		Baseline scan to occur w/in 30 minutes of dosing	

Part 2													
Study Period	Intervention (RHC Period)											Notes	
	Panel A = Period 2 Panel B, C and D = Period 3												
	Day 1	Day 1	Hour										
Scheduled Hour, Day	Pre RHC	Pre dose	0	0.25	0.5	1	2	3	4	4.5	24h or prior to D/C		
Administrative Procedures													
RHC Inclusion/Exclusion Criteria		X										Pre-dose assessment applies to Period 2 if Panel A and Period 3, if Panel B, C or D	
Prior/Concomitant Medication Review	X-----X												
MK-5475 Administration			X										
Inspiratory Flow Meter Assessment		X										Assessment to be done within 3 hours at predose (Panels B, C and D). An optional predose assessment may be done for Panel A.	
Standard Meals							X				X	See section 5.3.1 for timing of meals and snacks	
Domiciling	X-----X												
Pharmacodynamic Procedures													
Right Heart Catheterization (RHC) Measurements		X			X	X	X	X	X	X		See section 8.7.1 and operations manual for RHC details	
Pulmonary Arterial Pressure (PAP)		X	X-----X									q 30 minutes	
Arterial O ₂ Saturation (pulse oximetry)		X			X	X	X	X	X	X		On room air	
Mixed Venous O ₂ Saturation (MVO ₂)		X			X	X	X	X	X	X		On room air	
Safety Procedures													
Full physical examination	X										X	Pre RHC PE may occur w/in 24 hours of dosing	
Heart Rate (HR) & Blood Pressure (BP)	X	X			X-----X						X	HR/BP q 30 minutes	
Body Temperature (Temp)	X										X	See section 8.3.2 for all appropriate vital sign procedures.	
Respiratory Rate (RR)	X				X	X	X	X	X	X	X		
12-lead ECG	X										X	X	See section 8.3.3 for ECG procedure details

Part 2													
Study Period	Intervention (RHC Period) Panel A = Period 2 Panel B, C and D = Period 3											Notes	
	Day 1	Day 1	Hour										

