2.2.2 Preclinical and Clinical Studies

Refer to the Investigator's Brochure for detailed preclinical and clinical information on MK-5475.

As noted, there were few findings noted in rat studies. In dogs, dose-dependent heart rate and blood pressure changes were noted during systemic intravenous delivery only. In dog studies utilizing inhaled delivery, a dose-dependent slight thickening of the bronchial adventitia was noted, and this finding was used to establish the dog NOAEL.

Completed Clinical Studies

As of May 2020, MK-5475 has been evaluated in 2 completed clinical studies (PN001 and PN003). Data for these studies are summarized below.

In the first in human study of 16 healthy male participants (PN001), single dose MK-5475 ranging from 15 to 165 µg was generally well-tolerated. AEs reported were self-limiting and ranged from mild to moderate in intensity. No SAEs or events of clinical interest were observed. Most frequently reported AEs were headache and oropharyngeal pain.

No clinically important findings were observed in vital signs, ECGs, routine lab safety tests, pulmonary function tests and physical exams.

Single-dose PK data in PN001 showed that MK-5475 has a median Tmax of 1 hour at doses ranging from 15-165 µg. The geometric mean terminal half-life (t1/2) is approximately 2 hours across doses. Plasma exposures (AUC and Cmax) of MK-5475 appeared to show a linear upward trend in relationship to increasing doses. Maximum AUC0-24 observed was 1.47 nM*hr which is approximately three times below the dog NOAEL exposure (4.5 nM*hr). It is expected based on preclinical data and translational PK modeling that steady state will be achieved within 24 hours post the first dose.

Assessment of pulmonary blood volume (PBV) performed via functional respiratory imaging (FRI) at the 165 µg dose level showed an increase in pulmonary blood volume from baseline measures of 7.1 and 6.2% at 1 and 3 hours post dose, respectively, when compared to placebo.

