3 HYPOTHESES, OBJECTIVES, AND ENDPOINTS

Hypotheses are aligned with objectives in the Objectives and Endpoints table.

This study is to be conducted in male and female participants with group 1 pulmonary arterial hypertension (PAH).

Objectives	Endpoints
Primary	

 To evaluate the safety and tolerability of MK-5475 in participants with pulmonary arterial hypertension (PAH). (All parts) 	Safety and tolerability will be evaluated during clinical assessments that include vital signs, safety laboratory testing, physical examinations, ECG readings, PFTs and review of adverse events.

 To assess the duration and effect following a single inhaled dose of MK-5475 on pulmonary vascular resistance (PVR) in participants with pulmonary arterial hypertension (PAH). (Part 2, Period 2 (Panel A) and Period 3 (Panels B, C and D)) 	Peak reduction from baseline in PVR after a single inhaled dose of MK-5475
Secondary	

 To estimate the effect of MK-5475 given as single inhaled doses on systemic hemodynamic parameters (heart rate (HR), systolic and diastolic blood pressure (BP)) in participants with pulmonary arterial hypertension. (Part 2 Period 2 (Panel A) and Period 3 (Panels B, C and D)) 	
 HR and BP change from baseline at 0.5, 4.5, and 24 (or prior to discharge) hours post-dose.

 To obtain preliminary plasma pharmacokinetic (PK) data of MK-5475 (e.g. area under the curve (AUC) 0-24, AUC 0-∞, C_{max}, C₂₄, T_{max}, t_{1/2}) in participants with pulmonary arterial hypertension. (Part 1 and 2) 	
 AUC 0-∞, AUC 0-24, C_{max}, C₂₄, T_{max}, apparent terminal half-life

 To assess the effect following a single inhaled dose of MK-5475 on pulmonary blood volume (PBV) in participants with pulmonary arterial hypertension. (Part 2, Period 3 (Panel A) and Period 2 (Panels B, C and D)) 	
 Increases from baseline PBV at 1, 3, 8 and 24 hours postdose.

Objectives	Endpoints
Tertiary/Exploratory	

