9.3 Hypotheses/Estimation

Primary Objectives:

- To evaluate the safety and tolerability of MK-5475 in participants with pulmonary arterial hypertension (PAH).
- To assess the duration and effect following a single inhaled dose of MK-5475 on pulmonary vascular resistance (PVR) in participants with pulmonary arterial hypertension (PAH).

Secondary Objectives:

- To estimate the effect of MK-5475 given as single inhaled doses on systemic hemodynamic parameters (heart rate (HR), systolic and diastolic blood pressure (BP)) in participants with pulmonary arterial hypertension.
- To obtain preliminary plasma pharmacokinetic (PK) data of MK-5475 (e.g. area under the curve (AUC) 0-24, AUC 0-∞, C_{max}, C₂₄, T_{max}, t_{1/2}) in participants with pulmonary arterial hypertension.
- To assess the effect following a single inhaled dose of MK-5475 on pulmonary blood volume (PBV) in participants with pulmonary arterial hypertension.

Exploratory Objectives:

- To explore the relationship of MK-5475 concentration and summarize changes in pulmonary vascular resistance, pulmonary arterial pressure, cardiac output/cardiac index (CO/CI), systemic vascular resistance, mixed venous oxygen saturation and arterial oxygenation in participants with pulmonary arterial hypertension.
- To explore the effect of single doses of MK-5475 on the ratio of change from baseline in pulmonary vascular resistance / change from baseline in systemic vascular resistance.
- •To explore the relationship between mean change differences in pulmonary vascular resistance (PVR) and baseline changes in pulmonary blood volume (PBV) following a single dose of MK-5475.

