9.4 Analysis Endpoints

Primary Pharmacodynamic

The primary pharmacodynamic variable in this study is PVR in Part 2, Period 2 (Panel A) and Period 3 (Panels B, C and D).

Primary Safety

The primary safety endpoints in this study include all types of AEs, in addition to laboratory safety assessments, ECGs, PFTs and VS.

Secondary Endpoints for PD

The secondary endpoints in this study include HR and BP.

- Increases from baseline PBV at 1, 3, 8 and 24 hours postdose in Part 2, Period 3 (Panel A) and Period 2 (Panels B, C and D).

Secondary Endpoints for PK

The secondary endpoints in this study include AUC_{0-24hr}, AUC_{0-inf}, C_{max}, C_{24hr}, T_{max} and apparent terminal t_{1/2} after administration of single doses in Panel A Periods 1-3 and Panels B, C and D, Period 1.

Exploratory Endpoints

- Mean pulmonary artery pressure (mPAP), systemic vascular resistance (SVR), cardiac output (CO)/cardiac index (CI) and mixed venous and arterial oxygenation in Part 2, Period 2 (Panel A) and Period 3 (Panels B, C and D).
- PVR/SVR change from baseline at 0.5 through 4.5 hours post-dose Part 2, Period 2 (Panel A) and Period 3 (Panels B, C and D).
- Change from baseline PVR and PBV at 1 and 3 hours postdose in Part 2, Periods 2 and 3.

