9.6 Statistical Methods

Primary (PVR): Fold change from baseline individual PVR in Part 2, RHC Period only will be calculated for each postdose time point. The largest reduction from baseline will be identified for each participant. These reductions will be natural log-transformed and mean and 95% confidence interval calculated based on a t-distribution at each dose-level. These will be exponentiated and expressed as percents to obtain the geometric mean and 95% CI for percent reduction in PVR.

Primary (Safety): Incidence of AEs will be descriptively summarized. Summary statistics and plots will be generated for the change from baseline values in the VS, ECG parameters, and selected laboratory safety parameters for participants, as deemed clinically appropriate. Depending on the safety parameter, the difference from baseline will either be computed on the original scale (raw change from baseline) or on the log scale and back-transformed for reporting (percent change from baseline). Summary statistics for the raw laboratory safety tests, ECGs, and/or VS may also be computed, as deemed clinically appropriate.

Secondary (HR and BP): Each of these parameters will be analyzed separately for Part 2, RHC period only. Individual PD parameters (HR, SBP, and DBP) will be natural log transformed and analyzed in a linear mixed effects model with fixed effects for dose, time (0.5, 4.5, and 24 hours), dose by time interaction and a random effect for participant. The dependent variable is: PD_postdose – PD_predose (PD=HR, SBP, DBP). An unstructured covariance matrix for each time point will be used to allow for unequal variances via the REPEATED statement in SAS PROC MIXED (a similar model would be acceptable using R) Kenward and Roger's method will be used to calculate the denominator degrees of freedom for the fixed effects (DDFM=KR). If the model fails to converge, a simpler covariance structure such as compound symmetry may be used. The difference in least squares means with 95% CI will be calculated for post dose of MK-5475 versus predose of MK-5475 at each dose level by time.

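### The primary PVR objective includes duration, but PVR is measured only to 4.5 h and its sole endpoint and analysis is the peak reduction

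*Combined protocol and SAP*

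**What the plan says.** The second primary objective, worded alike in 1.1, 3 and 9.3, begins "To assess the duration and effect following a single inhaled dose of MK-5475 on pulmonary vascular resistance (PVR". The endpoint set against it in section 3 is "Peak reduction from baseline in PVR after a single inhaled dose of MK-5475". Section 9.6 computes the fold change from baseline at each postdose time and then keeps one value per person: "The largest reduction from baseline will be identified for each participant". Those values are averaged on the log scale by dose. No endpoint or analysis refers to duration, time of offset or effect remaining at the last reading.

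In the Schedule of Activities (1.3), the row "Right Heart Catheterization (RHC) Measurements" is marked predose and at 0.5, 1, 2, 3, 4 and 4.5 h, with nothing in the 24 h or discharge column. Section 8.7.1 agrees: "The study-related portion of RHC will continue until completion of all measurements at the 4.5 hr postdose timepoint", and it allows an earlier stop if clinically indicated. Plasma sampling in that period also ends at 4.5 h. The exploratory endpoint in 9.4 has the same limit: "PVR/SVR change from baseline at 0.5 through 4.5 hours post-dose".

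PBV is followed for longer. Section 9.4 lists "Increases from baseline PBV at 1, 3, 8 and 24 hours postdose" as a secondary endpoint, measured in a separate dosing period with a washout of at least 7 days.

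**The concern.** A primary objective should lead to an endpoint, an analysis and data that can answer it. Here the effect half does and the duration half does not. The peak analysis discards timing, so even the course of PVR within the observed window is not reported as an estimate. Beyond 4.5 h there are no PVR data.

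The risk lies in what the report then says about duration. A small mean effect at 4.5 h could be described as an effect lasting about four hours. A large one could be described as a long duration that nobody observed. Either would appear under a primary objective with no rule in the plan to prevent it.

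**Working it through.** The plan states no PVR time course, expected PVR effect, definition of duration, or precision figure, so there is nothing of its own to reproduce. The check asks whether an effect could plausibly be over by 4.5 h, using the only two time courses in the documents as proxies.

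**Inputs (2.2.2, healthy volunteers)**
- Plasma: median Tmax 1 h; terminal half-life about 2 h (1.88 h quoted for Day 1 of the first-in-human study).
- PBV at 165 µg, compared with placebo: "showed an increase in pulmonary blood volume from baseline measures of 7.1 and 6.2% at 1 and 3 hours post dose".

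**Proxy 1: the effect follows plasma**
- Fraction of the 1 h level left at 4.5 h: 2^(−(4.5−1)/2) = 2^(−1.75) = 0.297.
- With half-life 1.88 h: 0.275.
- With decay counted from time 0 and half-life 2 h: 2^(−2.25) = 0.210 (0.190 with 1.88 h).
- Time to half of the 1 h level: 1 + 2 = 3.0 h. Time to 10%: 1 + 2·ln(10)/ln(2) = 7.6 h.

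**Proxy 2: the effect follows PBV, declining exponentially**
- k = ln(7.1/6.2)/2 = 0.0678 per h, so the effect half-life is ln(2)/k = 10.2 h.
- Fraction of the 1 h effect left at 4.5 h: exp(−3.5k) = 0.789. A linear decline gives 0.778, and the log-ratio scale gives 0.795.
- Time to half: 1 + 10.2 = 11.2 h. Time to 10%: 1 + ln(10)/k = 35.0 h.

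**Reading the two together**
- The range at 4.5 h is roughly 20-80%. The proxies already disagree inside the window: at 3 h plasma is at 50% of its 1 h level and PBV at 6.2/7.1 = 87%.
- If duration means return close to baseline (10% taken here as an illustration), the end point falls after the last PVR reading under both proxies.
- If it means time to half of peak, it is observed under the plasma proxy and censored under the PBV proxy.

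**Would a small 4.5 h effect show that the drug had worn off?** The peak reductions and SDs below are assumptions, because the documents give neither. The remaining reduction at 4.5 h is the peak times the fraction left:

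| Assumed peak reduction | Plasma proxy (log-scale size) | PBV proxy |
|---|---|---|
| 20% | 5.9 points (0.061) | 15.8 points |
| 30% | 8.9 points (0.093) | 23.7 points |
| 40% | 11.9 points (0.127) | 31.6 points |

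The 95% CI half-width on the log scale is t·SD/√n. The n values are Panel D's maximum (7) and Panels B and C together (4 + 8 = 12):

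| Assumed SD | n = 7 (t = 2.447) | n = 12 (t = 2.201) |
|---|---|---|
| 0.08 | 0.074 | 0.051 |
| 0.15 | 0.139 | 0.095 |

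At SD 0.15 and n = 7, none of the three plasma-proxy residuals could be separated from no effect. At SD 0.08 and n = 12, all three could. In the PBV case a 20% peak leaves |ln(0.842)| = 0.172, which exceeds every half-width shown. An interval that includes 1 at 4.5 h is therefore not evidence of return to baseline, although it is not inevitable either.

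**The case against.** Several points on the other side stand.

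- **The proxies are weak.** They are healthy-volunteer data, one of them two PBV values without reported variability, and nothing in the documents ties plasma level or PBV to the decay of PVR in patients. A reader might infer that the documents themselves imply 30-79% of the PVR effect is still present at 4.5 h. They do not. Those figures are an extrapolation, and the lower end moves to about 20% if decay starts at time 0.
- **Duration is not always censored.** A reader might infer that the trial can yield only a lower bound. That fails if duration is defined as time to half of peak, which the plasma proxy puts at about 3 h.
- **A significance rule would not help.** It is tempting to declare a duration of at least 4.5 h whenever the 4.5 h interval excludes 1. That would make duration depend on sample size in a study with no hypotheses (9.8). Part 2 is also open label, with no placebo dose in the catheter period and sedation permitted (6.3.3, 6.5), so drift alone could meet the rule.
- **Timing is flexible and PBV runs longer.** Section 8.11.6 lets the catheter times change, and 9.3 and 9.4 plan an exploratory comparison of PVR with PBV. No later catheter time is planned, however. The comparison covers 1 and 3 h only, and PBV is a different measure taken after a different dose.
- **No duration estimate is planned, so none can mislead.** That is true of the analysis section, but it confirms the gap: the objective still promises one.

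How long to keep an invasive catheter in place is a design judgement, and this point does not dispute it.

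**Conclusion.** The point holds as a mismatch between a stated primary objective and what the plan delivers. Followed exactly, the plan gives no estimate of the duration of the PVR effect, and it has no PVR data after 4.5 h. That much rests on the text alone.

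That time to return to baseline would be right-censored is probable, not certain. It rests on two proxy assumptions under which about 20-80% of the effect could remain at the last reading. The size for PVR in these patients is unknown.

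**What to change.** - **Sections 1.1, 3 and 9.3:** restate the objective as the effect on PVR and its time course over 4.5 h after a single inhaled dose.
- **Section 9.6, estimates:** add the geometric mean PVR ratio to baseline with 95% CI, by dose, at 0.5, 1, 2, 3, 4 and 4.5 h. Give the number measured at each time, since 8.7.1 allows early stopping, and note that these are uncontrolled pre-post estimates.
- **Section 9.6, duration:** state that PVR duration is censored at 4.5 h. Report the size of the effect remaining at 4.5 h with its interval, claim no PVR offset time beyond 4.5 h, and do not read an interval that includes 1 as return to baseline.
- **Later effect:** label any statement about it as PBV at 8 and 24 h, not PVR. Section 9.1 lists PBV at 1, 3 and 8 h only and should be aligned with 9.4 and 9.6.

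The by-time estimates use readings already scheduled, so no procedure is added. The cost is a less favourable stated claim on duration and a small amount of extra analysis.
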